8.1.6.2 Secondary Efficacy Variables

The secondary efficacy variables are divided into two groups. The first group includes ranked secondary endpoints, which are ranked by clinical importance. Statistical significance is assessed at the pre-specified alpha level (two-sided) in ranked endpoint order until the significant level exceeds the pre-specified alpha level. No additional statistically significant treatment differences could be declared if the preceding ranked endpoint fails to achieve the pre-specified alpha level. The second group includes all other additional secondary variables. All analyses of secondary endpoints will be performed using the ITT analysis set.

In general, continuous secondary efficacy variables will be analyzed using a Mixed-Effect Model Repeated Measure (MMRM) model including factors for treatment group, visit, visit by treatment interaction, and stratification variables, for the longitudinal continuous endpoints. The MMRM analysis is considered primary for inferential purposes.

Categorical secondary efficacy variables will be analyzed using the CMH test controlling for stratification variables. Non-responder imputation for missing data will be used for categorical secondary endpoints.

Analysis of Pattern Mixture Model (PMM) will be performed as sensitivity analyses for ranked secondary endpoints.

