The comparisons between each risankizumab dose versus placebo for the primary efficacy variable will be performed using the Cochran-Mantel-Haenszel (CMH) test adjusted by prior biologic use (0, 1, > 1) and Baseline steroid use (yes, no). Both of the co-primary efficacy endpoints will be tested at statistically significant of 0.025 for each of the risankizumab dose groups versus placebo to adjust for multiplicity. A CMH based two-sided 95% confidence interval for the difference between treatment groups will be calculated.

The intent-to-treat (ITT) set includes all randomized subjects who have taken at least one dose of study drug. The primary population for efficacy analysis are the subjects in the intent-to-treat analysis set who had baseline eligibility SES-CD of ≥ 6 (≥ 4 for isolated ileal disease). Subjects who discontinue prior to Week 12 for any reason will be considered as "not-achieved" for CDAI clinical remission and endoscopic response endpoints.

In general, continuous secondary efficacy variables will be analyzed using a Mixed-Effect Model Repeated Measure (MMRM) model including factors for treatment group, visit, visit by treatment interaction, and stratification variables, for the longitudinal continuous endpoints. The MMRM analysis is considered primary for inferential purposes.

Pharmacokinetics and Immunogenicity:

Serum risankizumab concentrations will be summarized at each time point for each dosing regimen using descriptive statistics. Population pharmacokinetic analyses combining the data from this study and other studies may be performed. Relationships between risankizumab exposures and efficacy and safety variables of interest may be explored.

ADA incidence will be summarized by cohorts and study visits. ADA titers will be tabulated for each subject at the respective study visits. The effect of ADAs on risankizumab pharmacokinetics, efficacy and/or safety variable(s) and/or any additional analyses will be explored.

Safety:

Adverse events, laboratory data and vital signs are the primary safety parameters in this study. All safety comparisons will be performed between treatment groups using the safety set. Treatment emergent AEs are defined as events that begin or worsen either on or after the first dose of the study drug and within 140 days after the last dose of the study drug for subjects who do not participate in Study M16-000 or until first dose of study drug in Study M16-000 if the subject is enrolled in Study M16-000.

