5.3.3.2 Secondary Variables

Ranked Secondary Endpoints:

1. Proportion of subjects with clinical remission at Week 12
2. Proportion of subjects with CDAI clinical response at Week 4
3. Proportion of subjects with CDAI clinical response at Week 12
4. Change from baseline of Functional Assessment of Chronic Illness Therapy-Fatigue (FACIT fatigue) at Week 12
5. Proportion of subjects with CDAI clinical remission at Week 4
6. Proportion of subjects with CDAI clinical response and endoscopic response at Week 12

7. Proportion of subjects with SF remission at Week 12
8. Proportion of subjects with AP remission at Week 12
9. Proportion of subjects with endoscopic remission at Week 12
10. Proportion of subjects with enhanced clinical response at Week 4
11. Proportion of subjects with ulcer-free endoscopy at Week 12
12. Proportion of subjects with enhanced clinical response at Week 12
13. Proportion of subjects with resolution of extra-intestinal manifestations (EIMs) at Week 12, in subjects with any EIMs at Baseline
14. Proportion of subjects with CD-related hospitalization through Week 12
15. Proportion of subjects without draining fistulas at Week 12 in subjects with draining fistulas at Baseline

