8.2 Determination of Sample Size

The co-primary endpoints are the proportion of subjects with CDAI clinical remission at Week 12 and proportion of subjects with endoscopic response at Week 12.

A total of approximately 855 subjects will be randomized into two risankizumab treatment groups and the placebo group in a 2:2:1 ratio (342 subjects for risankizumab 600 mg dose group, 342 subjects for risankizumab 1200 mg dose group, and 171 subjects for placebo group). Assuming the Week 12 CDAI clinical remission rate will be 37% for one of the risankizumab dose groups and 17% for the placebo group, a sample size of 342 subjects for each of the risankizumab dose groups and 171 for the placebo group will have 99% power to detect the treatment difference between the risankizumab dose groups and placebo in CDAI clinical remission rates at Week 12 using Fisher's exact test at alpha of 0.025 (two-sided). Assuming the Week 12 endoscopic response rate will be 25.5% for one of the risankizumab dose groups and 8% for the placebo group, this sample size will have 99% power to detect the treatment difference between the risankizumab dose groups and placebo in endoscopic response rates at Week 12 using a Fisher's exact test at alpha of 0.025 (two-sided).

In addition, with sample size of approximately 540 bio-IR subjects, this study will have approximately 92% power for the bio-IR population to detect the treatment difference between one of the risankizumab dose groups and placebo in CDAI clinical remission rates at Week 12 using Fisher's exact test at alpha of 0.025 (two-sided) for the bio-IR population, assuming the Week 12 CDAI clinical remission rate will be 34% for the risankizumab dose groups and 15% for the placebo group. Similarly, with sample size of approximately 315 non-bio-IR subjects, this study will have 70% power to detect the treatment difference between one of the risankizumab dose groups and placebo in CDAI clinical remission rates at Week 12 using Fisher's exact test at alpha of 0.025 (two-sided) for the non-bio-IR population, assuming the Week 12 CDAI clinical remission rate will be 42% for the risankizumab dose groups and 21% for the placebo group for non-bio-IR subjects.

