8.3 Randomization Methods

A total of approximately 855 subjects will be randomized into two risankizumab dose groups and the placebo group in a 2:2:1 ratio (342 subjects for risankizumab 600 mg dose group, 342 subjects for risankizumab 1200 mg dose group, and 171 subjects for placebo

group). Randomization will be stratified by number of prior biologics failed (0, 1, > 1), the steroid use at Baseline (yes, no), and Baseline SES-CD (original, alternative), where the stratum of "original" includes the patients with baseline SES-CD of ≥ 6 (or ≥ 4 for subjects with isolated ileal disease), and the stratum of "alternative" includes the patients with baseline SES-CD of ≥ 3 to < 6 for ileocolonic or colonic disease or SES-CD of 3 for isolated ileal disease.

Subjects with clinical non-response to risankizumab at Week 12 will be re-randomized in a 1:1:1 ratio to 1200 mg IV dose group, 360 mg SC dose group, or 180 mg SC dose group. Subjects with clinical non-response to placebo at Week 12 will blindly receive 1200 mg risankizumab IV dose.

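### The primary MMRM for continuous secondary endpoints does not list the baseline value of the outcome; adding it would sharpen ranked endpoint 4 (FACIT-Fatigue change) at no cost

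*Protocol*

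**What the plan says.** Section 8.1.6.2 and the Statistical Methods part of the Synopsis give the same account of continuous secondary endpoints. They are in general analysed by a "model including factors for treatment group, visit, visit by treatment interaction, and stratification variables", for endpoints measured longitudinally. Both places add: "The MMRM analysis is considered primary for inferential purposes".

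One of the 15 ranked secondary endpoints in Section 5.3.3.2 is continuous, and it stands fourth: "Change from baseline of Functional Assessment of Chronic Illness Therapy-Fatigue (FACIT fatigue) at Week 12". Appendix C schedules FACIT-F at Baseline, Week 4 and Week 12.

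The stratification variables are set out in Section 8.3: "Randomization will be stratified by number of prior biologics failed (0, 1, > 1"), with steroid use at Baseline and the Baseline SES-CD stratum. None of them is a fatigue score. No current analysis section adds the baseline value of the outcome, and ANCOVA appears only in the abbreviation list.

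Section 8.1.6.2 also says that ranked endpoints are tested in order and that nothing further can be declared significant after a failure. Section 8.1 leaves complete analysis details to the SAP.

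**The concern.** The response is a change from baseline, and the baseline score is already collected. A change score subtracts the whole baseline value, including its measurement noise, whereas a regression on baseline subtracts only the part that predicts the Week 12 value. Leaving baseline out therefore gives a noisier treatment contrast. It also lets a chance difference in baseline fatigue between arms pass into the estimate.

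The position of this endpoint raises the stakes. Under the ordered testing in Section 8.1.6.2, a miss on FACIT-Fatigue would block formal claims on endpoints 5 to 15 for that dose. Precision at step four therefore bears on every later ranked endpoint.

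**Working it through.** **Inputs from the protocol.** Each comparison sets one active arm ("342 subjects for risankizumab 600 mg dose group", and the same number at 1200 mg) against 171 on placebo, so 342 + 171 = 513 subjects. The starting alpha is 0.025 two-sided per dose. Nothing is stated on the SD, effect, correlation or power for FACIT-F.

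**The plan's own figure.** The only powers stated are for binary endpoints. For CDAI clinical remission, Section 8.2 assumes "37% for one of the risankizumab dose groups and 17% for the placebo group", tested "using Fisher's exact test at alpha of 0.025 (two-sided"), and states 99%. Exact enumeration gives 99.5%, so the stated figure reproduces. It says nothing about FACIT-F.

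**Formulae.** Let σ0 and σ1 be the SDs at baseline and Week 12, and ρ their correlation (within strata, since strata are in the model).

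- Variance of a change score: σ0² + σ1² − 2ρσ0σ1
- Residual variance after adjustment for baseline: σ1²(1 − ρ²)
- Difference: (σ0 − ρσ1)², which is never negative and is zero only when ρ = σ0/σ1

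With equal SDs the first two become 2σ²(1 − ρ) and σ²(1 − ρ²), so the ratio of adjusted to unadjusted variance is (1 + ρ)/2. The allocation cancels. This is the Week 12 contrast with complete data.

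**Results for assumed ρ.**

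| ρ | Variance ratio (1+ρ)/2 | Fall in variance | Fall in SE, 1 − √ratio | Subjects needed without baseline to match 513 with it (513/ratio) |
|---|---|---|---|---|
| 0.3 | 0.65 | 35% | 19.4% | 790 |
| 0.5 | 0.75 | 25% | 13.4% | 684 |
| 0.7 | 0.85 | 15% | 7.8% | 604 |
| 0.8 | 0.90 | 10% | 5.1% | 570 |

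A simulation with 513 subjects and 4,000 runs gave variance ratios of 0.649, 0.741 and 0.863 for ρ of 0.3, 0.5 and 0.7, in line with the formula.

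**What this could mean for power.** Suppose, purely for illustration, that the unadjusted test had 80% power at two-sided alpha 0.025. The standardised effect is then 2.241 + 0.842 = 3.083. Dividing by √ratio and subtracting 2.241 gives, for ρ = 0.3, 3.083/0.806 − 2.241 ≈ 1.58, or 94.3% power. The other values of ρ give 90.6%, 86.5% and 84.3%. The 80% is an assumption, not a figure from the protocol.

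**Chance imbalance.** With equal SDs, the slope of change on baseline is ρ − 1. A baseline difference d between arms thus shifts the unadjusted estimate by −(1 − ρ)d, which is 0.7, 0.5, 0.3 or 0.2 of d in size for the four values of ρ. Adjustment removes this shift.

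**The case against.** The strongest reply is that this is SAP detail. The sentence opens with a general qualifier and says what the model includes, not that the list is closed. All the listed terms are categorical, so a continuous covariate might simply not have been mentioned among the factors. Section 8.1 defers specifics to the SAP. This stands as a reason for lower confidence: a reader might infer that the protocol excludes baseline, and it does not say so. It does not dispose of the point, because the protocol names the terms of a model and calls that model primary, and the listed terms do not supply baseline.

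Other stronger readings also fail:

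- **Invalid or biased analysis.** The comparison is randomised, so the change-score contrast is unbiased by design and type I error is unaffected. The co-primary endpoints are binary, are analysed by CMH, and are untouched.
- **A likely stop at endpoint 4.** Nothing shows FACIT-Fatigue to be near the margin. Its power is unknown, and Section 8.1.6.1 leaves the later alpha allocation to the SAP.
- **A broken missing-at-random assumption.** The model uses Week 4 values and the strata, and pattern-mixture sensitivity analyses are planned for ranked secondary endpoints. All that can be said is that the listed terms do not condition explicitly on baseline FACIT-F.
- **A large gain.** The 35% fall in variance belongs to the lowest correlation shown. At 0.8 it is 10%.
- **An error for endpoints with a single post-baseline assessment.** Section 8.1.6.2 confines the MMRM to longitudinal endpoints and leaves the others open.

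**Conclusion.** The point holds as a free improvement, with moderate confidence. The MMRM named as primary omits from its listed terms a covariate that is already collected. If it is run as listed, ranked endpoint 4 is tested validly but with less precision than the data allow.

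That adjustment does not worsen precision follows from the algebra, apart from the negligible cost of estimating one slope. The size depends on ρ, which is assumed. Over 0.3 to 0.8 with equal SDs, the standard error falls by about 19% down to 5%. With unequal SDs the gain differs, and it vanishes only at ρ = σ0/σ1. A miss at endpoint 4 would block later ranked claims for that dose, but how likely that is cannot be judged from the protocol. If the SAP already adds baseline, what remains is to align the protocol wording with it.

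**What to change.** In Section 8.1.6.2 and the Synopsis, add the continuous baseline value of the outcome and its interaction with visit to the MMRM terms, and state the same model in the SAP before database lock. Adding the baseline visit as a further repeated response with a free visit-by-treatment term would not recover the precision; a baseline covariate does.

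The cost is one phrase in two places. It needs no new data and no change to the sample size, and it does not affect type I error.

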8.1.7 Safety Analysis

Safety analyses will be carried out using the safety analysis sets, which includes all subjects who receive at least one dose of study drug. Incidence of AEs, including those related to study drug, changes in vital signs, physical examination results, and clinical laboratory values will be analyzed.

Adverse events will be coded using the Medical Dictionary for Regulatory Activities (MedDRA) dictionary. Treatment-emergent AEs are defined as AEs that began or worsened in severity after initiation of study drug and within 140 days after the last dose of the study drug. An overview of treatment-emergent AEs, including AEs leading to death and AEs leading to premature discontinuation (see details in the SAP), AEs by MedDRA preferred term and system organ class, AEs by maximum relationship to study drug, and AEs by maximum severity will be summarized by number and percentage.

Continuous laboratory and vital sign parameters will be summarized for each treatment group by visit. Treatment group differences between each of the risankizumab dosing groups and the placebo group for changes from Baseline may be analyzed using a one-way Analysis of Variance (ANOVA). Vital signs and laboratory data will be described by statistical characteristics and frequency of abnormal values. In addition, shift tables and listings will be provided for abnormal values, whereby the normal range of the analyzing laboratory will be used. Analysis details will be specified in the SAP.

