An overview of treatment-emergent AEs, AEs leading to death and AEs leading to premature discontinuation (see details in the statistical analysis plan [SAP]), AEs by Medical Dictionary for Drug Regulatory Activities (MedDRA version) preferred term and system organ class, AEs by maximum relationship to study drug, and AEs by maximum severity will be summarized by number and percentage.

Changes in laboratory data will be described using statistical characteristics and compared between treatment groups will be performed using a one-way Analysis of Variance (ANOVA). In addition, shift tables and listings will be provided for abnormal values, whereby the normal range of the analyzing laboratory will be used. Vital signs will be analyzed similarly.

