8.1.1.2 Safety Analysis Set

The safety analysis set consists of all subjects who received at least one dose of the study drug. The safety set will be analyzed as treated, according to treatment the subject actually received. The safety set will be used for safety analysis.

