8.1.6 Efficacy Analysis

8.1.6.1 Primary Efficacy Variables

The co-primary endpoints are the proportion of subjects who achieve CDAI clinical remission at Week 12 and proportion of subjects with endoscopic response at Week 12.

The comparisons between each risankizumab dose versus placebo for the primary efficacy variable will be performed using the Cochran-Mantel-Haenszel (CMH) test adjusted by number of prior biologics failed (0, 1, > 1) and steroid use at Baseline (yes, no). A multiple testing procedure will be used to provide strong control of the type 1 error rate at $\alpha = 0.05$ (2-sided) across analyses comparing each risankizumab dose level to placebo with respect to the co-primary endpoints, and ranked secondary endpoints. Specifically, testing will utilize a sequence of hypothesis testing for the co-primary endpoints followed by the ranked secondary endpoints, and will begin with testing each of the co-primary endpoints using α of 0.025 (2-sided) for each dose compared to placebo. If both co-primary endpoints achieve statistical significance within a dose level, continued testing will follow a pre-specified weight of α allocation between the single hypothesis within the family, as well as between the families of hypotheses across the doses. Details will be

provided in the Statistical Analysis Plan. A CMH based two-sided 95% confidence interval for the difference between treatment groups will be calculated. Subjects who discontinue prior to Week 12 for any reason will be considered as "not-achieved" for CDAI clinical remission and endoscopic response endpoints.

The analysis of co-primary efficacy endpoints will be performed in bio-IR and non-bio-IR population. Additional subgroup analyses will be outlined in the SAP. Sensitivity analyses for missing data handling using MI, PMM and OC will be performed for co-primary endpoints and details will be outlined in the SAP.

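### One-way ANOVA of laboratory and vital-sign changes from Baseline is valid, but gives away a little precision by not using the baseline value as a covariate

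*Protocol*

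**What the plan says.** The method is named twice.

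- Section 8.1.7 (Safety Analysis) provides by-visit summaries of continuous laboratory and vital-sign parameters. It then says that differences between each dose and placebo "for changes from Baseline may be analyzed using a one-way Analysis of Variance (ANOVA"). The wording is permissive, and the paragraph ends with "Analysis details will be specified in the SAP".
- The Synopsis (Section 1.2, Safety under Statistical Methods) is firm. Laboratory changes "compared between treatment groups will be performed using a one-way Analysis of Variance (ANOVA"), and "Vital signs will be analyzed similarly".

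Neither place mentions a baseline covariate. ANCOVA is in the abbreviation list, but neither safety text uses it.

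The same data are also displayed in other ways: "Vital signs and laboratory data will be described by statistical characteristics and frequency of abnormal values", with shift tables and listings of abnormal values. The analysis set is the safety set: "The safety set will be analyzed as treated, according to treatment the subject actually received". Strong type I error control in Section 8.1.6.1 applies "with respect to the co-primary endpoints, and ranked secondary endpoints", so it does not reach any laboratory or vital-sign comparison.

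**The concern.** Change scores are usually negatively correlated with their starting value: subjects who start high tend to fall, and subjects who start low tend to rise. Subtracting the baseline uses it with a fixed slope of 1. When the true slope of follow-up on baseline is below 1, subtraction over-corrects. The residual variance is then larger than it need be, and part of any chance difference between arms at baseline stays in the estimated treatment difference.

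The Synopsis counts laboratory data and vital signs, together with adverse events, as the main safety parameters of the trial. Placebo is the smallest arm and the comparator for both doses, so precision in these comparisons is worth having. Appendix C schedules vital signs, chemistry and hematology at Baseline, with screening laboratory results allowed to stand in when recent enough. Every subject with a change score therefore already has the covariate.

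A smaller matter goes with it. The Synopsis says *will* and Section 8.1.7 says *may*, so a reader cannot tell whether these tests are planned or optional.

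**Working it through.** **Inputs.** Arm sizes are those of Section 8.2: "a sample size of 342 subjects for each of the risankizumab dose groups and 171 for the placebo group". The safety set may be somewhat larger, because up to 85 subjects with lower SES-CD are also randomized; the ratios below do not depend on the arm sizes. The protocol gives no SD, correlation, precision or power for these comparisons, so there is no stated figure to reproduce. The correlation r between baseline and follow-up is an assumption, shown over a range.

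**Variance.** Let s be the common SD at baseline and follow-up, and k² = 1/171 + 1/342 = 0.00877, so k = 0.0937.

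- One-way ANOVA on change: Var = 2(1−r)·s²·k²
- ANCOVA: Var = (1−r²)·s²·k²
- Ratio, ANCOVA to ANOVA: (1−r²) / [2(1−r)] = (1+r)/2
- Ratio of interval widths: √[(1+r)/2]

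| r (assumed) | SE, ANOVA on change (in s) | SE, ANCOVA (in s) | Variance lower by | Interval narrower by |
|---|---|---|---|---|
| 0.3 | 0.111 | 0.089 | 35% | 19% |
| 0.5 | 0.094 | 0.081 | 25% | 13% |
| 0.7 | 0.073 | 0.067 | 15% | 8% |
| 0.9 | 0.042 | 0.041 | 5% | 2.5% |

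Read the other way, the standard error without the baseline term is 24%, 15%, 8% and 3% larger at these four values.

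**Unequal variances.** With SDs s₀ at baseline and s₁ at follow-up, the residual variance of the change score is s₀² + s₁² − 2r·s₀·s₁, and that of ANCOVA is s₁²(1−r²). The difference is (s₀ − r·s₁)². It is never negative, and it is zero only when the slope r·s₁/s₀ equals 1. So apart from one degree of freedom ANCOVA does not lose, but the gain can be smaller than in the table.

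**Chance imbalance.** If the arms differ at baseline by d, the difference in mean change is shifted by (1−r)·d in the opposite direction. For an imbalance of one standard error (d = 0.0937 s):

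- r = 0.5: 0.5 × 0.0937 = 0.047 s, which is 0.50 of the SE of the change difference
- r = 0.7: 0.3 × 0.0937 = 0.028 s, or 0.39 SE
- r = 0.9: 0.1 × 0.0937 = 0.009 s, or 0.22 SE

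ANCOVA removes this shift, which is conditional on the imbalance that happened to occur.

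**Validity of the stated model.** In 20,000 simulated null trials with 171 and 342 subjects, the unadjusted comparison of changes rejected at nominal 5% in 4.9% of trials at r = 0.5 and in 5.3% at r = 0.7. The Monte Carlo standard error is √(0.05 × 0.95/20,000) = 0.15 percentage points, so both are compatible with 5%. The mean estimated difference was about 0 in both settings.

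**The case against.** The strongest reply is that a covariate in a safety summary model belongs in the SAP. Section 8.1.7 is permissive and expressly defers details, and the SAP is not at hand, so the final model may already contain baseline. This stands in part: nobody can say from the protocol that baseline will be absent. But the protocol does not leave the method open. It names a model without a baseline term in two places, once firmly, and a SAP that used ANCOVA would depart from the Synopsis.

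A second reply is that nothing hangs on these comparisons. They lie outside the multiplicity procedure, carry no stated hypothesis or decision rule, and do not enter the sample size. Shift tables, abnormal-value frequencies and listings, which are better suited to finding outlying individuals, do not depend on the ANOVA. All of this stands, and it limits the weight of the point.

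A third reply is that ANCOVA is not free of assumptions: it supposes a linear relation with a common slope, across many parameters. That is fair, but the change score also imposes a common slope, fixed at 1.

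A reader might go further and infer that the planned comparison is biased, or that a baseline imbalance passes into it in full. The documents do not support that. Treatment is randomized, change from Baseline already removes the share r of an imbalance, and what remains averages to zero over randomization.

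**Conclusion.** The point holds as a minor efficiency improvement. The stated one-way ANOVA is valid but less precise than an analysis using the baseline value already collected. The gain is 25%, 15% and 5% in variance, or about 13%, 8% and 2.5% in interval width, at r = 0.5, 0.7 and 0.9. It rests on equal variances at baseline and follow-up and on an assumed r, which will differ between parameters; for a parameter with high r the gain is negligible. The unbiasedness argument supposes that treatment received, by which the safety set is analyzed, agrees closely with treatment assigned.

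It would be wrong to read this as an error of validity, or as a sign that a safety conclusion of the trial would change: no stated decision rests on these comparisons. The difference between *will* and *may* is a genuine inconsistency, but an editorial one, since both places name the same model.

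**What to change.** In Section 8.1.7 and in the safety part of the Synopsis, replace the one-way ANOVA by an ANCOVA of change from Baseline, with treatment group as factor and the baseline value of the same parameter as covariate. The baseline value should be the one from which the change is computed, including a screening laboratory result where that stands in. Use the same verb in both places, so that it is clear whether the comparisons are planned or optional.

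The cost is a text edit in two places, one covariate in the program and one degree of freedom. No new data are needed, and no subject with a change score drops out. The only methodological price is the usual assumption of linearity and a common slope. The descriptive displays, shift tables and listings stay as they are.
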